7.4.1. Pregnancy test

Where indicated a urine dip stick test will be carried out at visit 1 (Face-to-face screening visit). This will be conducted prior to any other assessments. If positive the patient will be a screen failure and no further data will be collected. If the chronology allows, the patient may be rescreened post-partum if they are not breastfeeding the child.

7.4.2. Visit 1 – Face to face screening visit (day -28 up to -1)

Following informed consent, a negative pregnancy test, and confirmation of eligibility, data will be captured at visit 1 (screening) prior to randomisation within the clinical data management system (CDMS), including the following:

- Sex at birth
- Age
- Ethnicity
- Home postcode to calculate index of multiple deprivation
- Current employment details, or reason for not working.
- Income, or details of benefits received.
- Highest level of education

- Relevant past medical history including: systems enquiry; allergies; current treatment and medications; any non-drug therapies; analgesia use in the last month and reason.
- TMD history including: duration of M-TMD to nearest month; other (known) TMD diagnoses; TMD treatment history and dates of treatment to nearest month.
- Migraine history using ID Migraine to screen. A positive screen will result in collection of details on: number of headache days per month categorised into <10days, 10-15 days, >15 days, any accompanying symptoms to the headache, and a MIDAS questionnaire.

The CRF will also capture the diagnoses elicited from the clinical review and examination derived from the Diagnostic Criteria for TMD (Schiffman et al., 2014). A routine extra and intra-oral examination will be conducted examining: cranial nerves V and VII, temporomandibular joint including pain-free opening and maximum unassisted opening, masseter and temporalis, cervical lymph nodes, salivary glands, screening of intra-oral soft and hard tissues to note any gross and relevant mimicking or serious pathology and not including periodontal examination. Vital signs will be recorded including weight, height, blood pressure, and pulse.

Research assessments as detailed in the schedule of events will be conducted prior to randomisation following confirmation of eligibility.

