7.4.6.2. Characteristic pain intensity (CPI) and Graded Chronic Pain Scale

The CPI is a validated three-item self-report instrument derived from the Graded Chronic Pain Scale examining current, average and worst pain intensity on a numerical rating scale of 0 (no pain) to 10 (worst pain imaginable) in the last three months. The instrument's total minimum score is 0 and maximum is 100 which are derived by taking the mean of the three responses and multiplying by 10.

The Graded Chronic Pain Scale will be used in full at screening and consists of 7 items. Three of the items are the CPI and the remaining four are related to disability experienced because of the persisting pain. Three of the disability items use the same numerical rating scale as the CPI and the other uses a four-choice categorical response. The GCPS produces five ordinal outcomes via an algorithm: I (lowest pain-related disability), IIa, IIb, III, IV (highest pain related disability).

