The co-primary outcomes of disorder specific quality of life measured by OHIP-TMD, and pain intensity measured by CPI at 36wks will each be compared between treatment groups using separate linear mixed effects regression models with nested random effects for site and participant and fixed effects for treatment, timepoint, treatment by timepoint interaction, baseline score and the stratification factor of psychosocial status. These models will each include the outcome data at all timepoints which will help account for missing data (under a missing at random assumption). These models will each be used to calculate mean differences at 36 weeks (BTX - TAU and Lidocaine injections - TAU) and associated two-sided 95% confidence intervals (CIs) for each coprimary outcome to test the superiority of BTX and Lidocaine injections compared to TAU. Superiority will be concluded if the upper limit of the two-sided 95% CIs are both less than 0. To conclude that BTX or Lidocaine are effective, statistically significant differences in both co-primary outcomes compared to TAU will be needed. This analysis will be conducted in the ITT population.

These models will also each be used to estimate the mean differences (BTX - TAU and Lidocaine injections - TAU) and associated two-sided 95% CIs for the secondary outcomes of disorder specific quality of life measured by OHIP-TMD, and pain intensity measured by CPI at 12 and 24 weeks.

²The hypothetical strategy targets the treatment effect in the hypothetical setting where the intercurrent event would not occur.

A secondary analysis will additionally adjust the estimates for OHIP-TMD by including fixed effects for the baseline covariates of GCPS and duration of pain that are known to be strongly related to outcome. This will also be done for CPI. However, as CPI is a component of the GCPS, baseline GCPS will not be included. We will consider alternative strategies to deal with the intercurrent events of treatment discontinuation and alternative treatments in the SAP.

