10.3. Sample Size Calculations

The sample size will be 663 which has been chosen to provide high power for both the OHIP-TMD and CPI co-primary outcomes (Durham et al., 2021; Dworkin et al., 2008; Yule et al., 2015; Collignon et al., 2020).

From Yule et al, the standard deviation (SD) of OHIP-TMD is 20.7 at 12 weeks (Yule et al., 2015), which we expect to be consistent at subsequent measurement times. The correlation with baseline was 0.6. To have 90% power (two-sided 5% type I error rate) to detect a difference between arms equal to the minimally important clinical difference (MICD) of 6.0 would require 251 per arm; taking the correlation into account would reduce this to $(1-0.6^2)*251 = 161$ per arm. We have inflated this by 27% to account for worst-case scenario loss-to-follow up identified between two large research studies we have conducted involving treatment and M-TMD (Durham et al., 2021; Yule et al., 2015). This gives a required sample size of 663.

This sample size provides extremely high power (>99%) to detect differences between arms in the CPI, which we assume has an SD of 20 based on the DEEP study (Durham et al., 2021) and MICD of 10 (Dworkin et al., 2008). To conclude superiority, statistically significant differences in both OHIP-TMD and CPI will be needed, meaning that an adjustment for multiple testing is not required and that the overall power is approximately 90% for each separate comparison (BTX vs TAU and Lidocaine vs TAU). As per consensus on multi-arm trials with distinct interventions, we do not formally adjust for multiple intervention arms (Collignon et al., 2020), but the total chance of recommending an ineffective intervention as superior to TAU is <5%. The quantity and timing of attrition will be monitored. If the attrition rate by 36 weeks increases above the estimated 27%, we may increase the sample size to maintain the power of the trial in agreement with the trial's oversight committees and subject to funding and time constraints.

11. Economic Analysis

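### The primary OHIP-TMD model leaves out baseline GCPS and pain duration, which the protocol calls strongly prognostic and already collects: a missed efficiency, not an error

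*Protocol*

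**What the plan says.** Section 10.2.1 of the protocol sets out a linear mixed model for each co-primary outcome. Site and participant enter as nested random effects. The remaining terms are listed as "fixed effects for treatment, timepoint, treatment by timepoint interaction, baseline score and the stratification factor of psychosocial status". Superiority is judged from these models.

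The same section then describes a secondary analysis of OHIP-TMD that adds the "baseline covariates of GCPS and duration of pain that are known to be strongly related to outcome". For CPI the secondary analysis adds duration only. GCPS is kept out there because CPI is one of its components. That is the only reason for an exclusion that the section gives, and it concerns CPI, not OHIP-TMD.

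Both covariates are available for the main analysis. Section 7.4.6.2 states: "The Graded Chronic Pain Scale will be used in full at screening". Section 7.4.2 lists "duration of M-TMD to nearest month" among the screening data captured before randomisation. Section 10.2 defines baseline as data collected at screening before randomisation.

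The sample size in section 10.3 takes credit for one covariate only, the baseline OHIP-TMD score: "The correlation with baseline was 0.6".

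**The concern.** The protocol fixes the primary covariate list itself, and the list sits awkwardly with its own statement about prognosis. If two pre-randomisation variables are strongly related to outcome, including them in a linear model would normally narrow the confidence interval for the treatment difference. It would leave the estimand, a mean difference at 36 weeks, unchanged.

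The place where this could matter is OHIP-TMD. A treatment is declared effective only if both co-primaries succeed. Section 10.3 puts CPI power above 99%, so overall power is essentially the OHIP-TMD power of about 90%. Any further explained variance in OHIP-TMD is a gain over plan. What is at stake is some precision on the limiting outcome.

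**Working it through.** **Inputs from section 10.3.** Two-sided alpha 5%, power 90%; "the standard deviation (SD) of OHIP-TMD is 20.7 at 12 weeks"; "minimally important clinical difference (MICD) of 6.0 would require 251 per arm"; baseline correlation 0.6; loss to follow-up 27%; for CPI, SD 20 and difference 10.

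**Step 1: reproduce the plan's figure.**
- Per arm, unadjusted: n = 2(1.960 + 1.282)² × 20.7² / 6.0² = 250.1, rounded up to 251.
- With the baseline correlation: (1 − 0.6²) × 251 = 160.64, so 161.
- With 27% loss: 161 / 0.73 = 220.5, so 221 per arm, and 3 × 221 = 663.

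The planned total reproduces exactly without GCPS or duration.

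**Step 2: current power on OHIP-TMD.** Residual SD = 20.7 × √(1 − 0.36) = 16.56. With 161 completers per arm, SE = 16.56 × √(2/161) = 1.846. Power = Φ(6/1.846 − 1.960) = 90.2%. A t-based calculation gives 90.0%.

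**Step 3: power with the extra covariates.** Let R² be the share of the remaining residual variance that GCPS and duration explain, given what is already in the model. The protocol gives no value, so this is an assumption and a range is shown. The residual SD becomes 16.56 × √(1 − R²).

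| Assumed R² | SE | Change in SE | OHIP-TMD power |
|---|---|---|---|
| 0 | 1.846 | – | 90.2% |
| 0.01 | 1.836 | −0.5% | 90.4% |
| 0.02 | 1.827 | −1.0% | 90.7% |
| 0.05 | 1.799 | −2.5% | 91.6% |
| 0.10 | 1.751 | −5.1% | 92.9% |
| 0.15 | 1.702 | −7.8% | 94.1% |
| 0.20 | 1.651 | −10.6% | 95.3% |

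**Step 4: cost in degrees of freedom.** Section 7.4.6.2 gives GCPS five grades, so it uses 4 degrees of freedom. Duration in one continuous form uses 1, making 5 in all. With 3 × 161 = 483 completers and about 5 already used, the variance factor is 478/473 = 1.0106, an inflation of about 1.1%. At R² = 0.01 the net factor is 0.99 × 1.0106 = 1.0005, so the gain is cancelled. At R² = 0.05 it is 0.95 × 1.0106 = 0.960, so most of the gain remains. The powers in the table do not include this cost.

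**Step 5: CPI.** With SD 20, difference 10 and 161 per arm, power is 99.4% even without credit for baseline CPI. Across the same range of R² for duration it is 99.5% to 99.9%, a change of at most 0.5 percentage points.

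These steps treat the 36-week comparison as a simple adjusted comparison of completers. They take no account of what the mixed model recovers from the 12- and 24-week data.

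**The case against.** The strongest reply is that nothing here is wrong. The primary model already contains both stratification factors and the one predictor whose strength the protocol quantifies. Design and analysis agree, 663 reproduces, and the fuller adjustment is already pre-specified as secondary. All of that stands, and it is why the point concerns efficiency only.

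The reply also has force on size. A strong relation to outcome is not the same as a strong relation after baseline OHIP-TMD has removed 36% of the variance. Pain grade probably shares information with that score and with psychosocial stratum, so the true gain could lie near the bottom of the range, where it is nil after Step 4.

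A reader might infer more than the documents support in four ways:
- **Two competing estimates.** Section 10.2.1 attaches the superiority rule to the primary model and labels the other analysis secondary. The order is fixed in advance.
- **A saving in participants.** An assumed R² of 0.05 or 0.10 corresponds to totals of 630 or 597 in place of 663, but this only restates the assumption. The protocol gives no figure on which to reduce the sample.
- **A repair to the missing-at-random assumption.** Dropout might depend on pain grade or chronicity, in which case conditioning on them would help. That is plausible, but nothing in the protocol shows it, and the model already uses the 12- and 24-week outcomes.
- **An equal problem in both models.** GCPS is deliberately kept out of the CPI analyses for a stated reason, and CPI has power to spare.

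The use of duration as an exploratory subgroup factor in section 10.2.4, split at 60 months, does not prevent its use as a main effect.

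**Conclusion.** The point holds as a missed efficiency on the limiting co-primary. The primary OHIP-TMD model omits two covariates that the protocol calls strongly prognostic and collects before randomisation, and no reason is given for that model. Validity, type I error and the planned 90% power are unaffected.

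The gain is from about 90% to between 90.4% and 95.3% power, before the cost in degrees of freedom, if GCPS and duration explain a further 1% to 20% of residual variance. That range is assumed. The calculation also rests on the protocol's SD, correlation and attrition figures. The gain on CPI is negligible.

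**What to change.** In section 10.2.1:
- Add baseline GCPS grade, as a categorical variable, and pain duration, in one pre-specified continuous form such as log months, as fixed effects in the primary OHIP-TMD model.
- Add pain duration in the same form to the primary CPI model for consistency. Leave GCPS out of it, as the protocol states.
- Keep the present models as the sensitivity analysis.
- Pre-specify how missing covariate values are handled, with a rule suited to each: for example, a missing category for the ordinal grade and a single-imputation rule for duration. Mean imputation does not suit a five-level grade.

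If the present model is preferred, a sentence explaining why covariates called strongly prognostic are left out would settle the matter.

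The change should be made before comparative results are seen. Section 7.2 allows the trial statisticians access to unblinded data for monitoring reports. If they have already seen unblinded outcome data, the blinded statistical methodology lead should sign the change off, by the route that section describes. Whether that stage has been reached cannot be seen from the protocol.

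The cost is an amendment to the analysis text, a choice of functional form, a missing-value rule and up to 5 degrees of freedom out of about 483 completers. No new data are needed.

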10.2.2. Analysis of Secondary Outcome Measures

Secondary outcomes will be analysed for superiority of each intervention against TAU. All analyses will be in the ITT population i.e. following a treatment policy approach. Estimated differences between treatment groups will be reported with two-sided 95% confidence intervals.

Secondary patient-reported outcomes (PHQ-4, BPSQI, SF-JFLS, GIC, Liverpool adverse effects profile, FaCE) will be analysed using linear mixed effects regression models similar to the co-primary outcomes above, but with the baseline value of the corresponding outcome included as a fixed effect. Domains or individual items may also be reported and analysed using appropriate regression techniques as described in the SAP. Analgesia use at any time during the trial will be analysed as a binary outcome using mixed effects logistic regression with a random effect for site and fixed effects for treatment and the stratification factor of psychosocial status. The secondary outcomes of 30% and 50% reduction from baseline in CPI and OHIP-TMD will be analysed separately at each timepoint using mixed effects logistic regression with a random effect for site and fixed effects for treatment, baseline score and the stratification factor of psychosocial status.

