7.4.6.7. Global impression of change (GIC)

The validated Patient Global Impression of Change scale (Dworkin et al., 2005; Guy, 1976) asks the patient to compare a construct following treatment to prior to treatment and employs a seven-point response scale (scoring in parentheses): very much improved (3) through no change (0) to very much worse (-3). The constructs examined through four items will be: pain intensity; ability to conduct daily

activities; emotional state; overall status. Patients will be asked to select a level of change from the seven-point scale in response to the prompt, "Since the start of the study my [insert construct] is".

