7.4.6.10. Facial Clinimetric Evaluation (FaCE) scale

This is a validated 15-item instrument examining 6 domains related to facial nerve paralysis: facial movement, facial comfort, oral function, eye comfort, lacrimal control, social function (Kahn et al., 2001). It employs a five-point response scale: strongly agree (1) through don't know (3) to strongly disagree (5). Its total score ranges from 0 (most affected) to 100 (not affected) and is calculated by an algorithm. The scale will only be used if patients opt into its use due to their perception of a facial weakness after an injectable therapy has been applied.

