10.2. Statistical Analyses

The analysis of all outcome measures will be described in detail in a pre-specified Statistical Analysis Plan (SAP) that will be reviewed by the trial's oversight committees and signed off by the CI prior to any comparative analyses being undertaken. Any changes to the statistical analysis plan made afterwards will be documented and reviewed by the senior methodological lead who has not had access to the results of the comparative analyses. Throughout the statistical section (section 10.2), baseline refers to data collected before randomisation at the screening visit.

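### Section 10.2.2 adjusts GIC, LAEP and FaCE for a baseline value that none of them has, and plans a comparison with TAU on FaCE that its collection rule does not allow

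*Protocol*

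**What the plan says.** Protocol section 10.2.2 sets a general rule: "Secondary outcomes will be analysed for superiority of each intervention against TAU". It adds: "All analyses will be in the ITT population i.e. following a treatment policy approach". It then names the instruments and the model: "Secondary patient-reported outcomes (PHQ-4, BPSQI, SF-JFLS, GIC, Liverpool adverse effects profile, FaCE) will be analysed using linear mixed effects regression models". These models resemble the co-primary ones "but with the baseline value of the corresponding outcome included as a fixed effect". Section 10.2 fixes the meaning of the term for the whole statistical section: "baseline refers to data collected before randomisation at the screening visit".

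The collection rules are elsewhere:

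- **GIC (7.4.6.7).** It "asks the patient to compare a construct following treatment to prior to treatment", and its prompt refers back to the start of the study.
- **LAEP (7.4.6.8).** It covers adverse events while on medication over the past month. The schedule of events (7.4.10) enters it at weeks 12, 24 and 36 only.
- **FaCE (7.4.6.10).** It is used only if patients choose it "due to their perception of a facial weakness after an injectable therapy has been applied". In the schedule it is optional at follow-up, at the patient's choice, and is otherwise tied to the unscheduled facial weakness visit.

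**The concern.** The analysis section names specific instruments and a specific covariate, and the schedule does not supply that covariate for half of them. A model that needs a covariate missing for every participant has no usable records.

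For GIC and LAEP the consequence is limited. Without the impossible term, a valid randomised comparison with TAU remains.

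For FaCE, removing the term is not enough. The score exists only where someone has perceived weakness and chosen to complete the form, and the rule in 7.4.6.10 ties that to an injection. A model fitted to whatever scores arrive would compare affected, self-selected people across arms, with little or nothing on the TAU side. Such a result could be reported as a superiority analysis in the ITT population when it is not one. Comparing adverse-effect profiles is a stated secondary objective (3.2 f), and facial weakness after Botox is a pre-specified event of interest (9.3), so a misleading contrast here would matter for interpretation.

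**Working it through.** The plan gives no figure on this point. The check sets the six instruments in 10.2.2 against the schedule (7.4.10), using the definition of baseline in 10.2.

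| Instrument | Entry at screening | Follow-up entries | Own baseline available |
|---|---|---|---|
| PHQ-4 | yes | weeks 12, 24, 36 | yes |
| BPSQI | yes | weeks 12, 24, 36 | yes |
| SF-JFLS | yes | weeks 12, 24, 36 | yes |
| GIC | no | weeks 12, 24, 36 | no |
| LAEP | no | weeks 12, 24, 36 | no |
| FaCE | no | optional, or at an unscheduled visit | no |

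Three of six have the covariate and three do not (6 − 3 = 3). The instrument descriptions agree with the schedule, so this is not a misread table:

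1. **GIC.** It rates a construct after treatment against its state before treatment. Before randomisation there is nothing to rate, so a baseline is impossible by construction.
2. **LAEP.** A pre-treatment administration is conceivable, but the protocol plans none.
3. **FaCE.** Its use follows a perceived weakness after an injection. Under 7.4.6.10 a pre-randomisation value cannot arise.

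Next, the contrast required for FaCE. The general rule in 10.2.2 asks for BTX − TAU and lidocaine − TAU among participants analysed as randomised.

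- Under 7.4.6.10 taken alone, the expected number of TAU participants with a FaCE score is zero, and neither difference can be estimated.
- Section 7.4.5, the footnote to the trial flow diagram in section 4.1 and the schedule entry are worded for any participant, so an occasional TAU score is conceivable. TAU scores would then be few rather than none.
- In either case a score is recorded only after a post-randomisation event that treatment may cause. Those observed in one arm need not be comparable with those observed in another, whatever covariates are used. That is not a treatment-policy comparison of the randomised groups.

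Last, what is not touched. The co-primary models in 10.2.1 use OHIP-TMD and CPI, both measured at screening. The sample size in 10.3 reproduces and does not depend on these instruments: 251 × (1 − 0.6²) = 160.6, rounded up to 161 per arm; 161 / (1 − 0.27) = 220.5, rounded up to 221; 3 × 221 = 663.

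**The case against.** The strongest reply is that this is a wording slip in secondary analyses. Section 10.2.2 calls the models similar to the co-primary ones, not identical. Section 10.2 leaves full detail to a SAP signed off before any comparative analysis, and any statistician would drop a covariate that does not exist. For GIC and LAEP that costs no validity. FaCE is also absent from the secondary outcome list in 3.3.2, and facial weakness itself is captured as an adverse event and by House-Brackmann scoring, so the adverse-effect objective does not rest on FaCE.

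Most of this stands on severity. It does not remove the error. The sentence in 10.2.2 states what differs from the co-primary model, and that difference is the baseline term. What it defers to the SAP is the handling of domains and individual items. Dropping the covariate also leaves the FaCE selection problem where it was.

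Three stronger readings are tempting, and the documents do not support them:

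- **TAU has no FaCE scores at all.** Section 7.4.6.10 points that way, but the arm-neutral wording in 7.4.5, the flow diagram footnote and the schedule allows a few.
- **The size of the FaCE subset or the precision lost on LAEP can be calculated.** The protocol gives no rate of opting in to FaCE and no correlation between LAEP before and after treatment. The 0.6 in 10.3 belongs to OHIP-TMD, a different construct.
- **A randomised comparison of facial weakness is already available from existing data.** The schedule lists a cranial nerve examination for everyone, but 7.4.4 has the case report forms capture facial nerve weakness by House-Brackmann only in those receiving an injectable. Equivalent recording in TAU is not established.

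**Conclusion.** The point holds as an internal contradiction in the protocol. Three of the six models in 10.2.2 cannot be fitted as written because the own-baseline covariate does not exist. For GIC and LAEP this is a specification error with a simple repair and no bias. For FaCE the planned superiority comparison with TAU in the ITT population is not possible: TAU scores would be few or none, and all scores come from a subset selected after randomisation.

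The conclusion rests on the schedule and the instrument sections being the intended collection rules. It needs no assumption about event rates or correlations. It concerns secondary and supplementary measures only; the co-primary estimates, the superiority rule and the sample size of 663 are unaffected.

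**What to change.** Amend 10.2.2, and carry the same text into the SAP:

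1. **GIC and LAEP:** same mixed model without an own-baseline term, keeping the psychosocial stratum.
2. **FaCE:** remove it from the list of superiority models. Report it descriptively, by arm, among participants who report facial weakness, and state that these summaries are not a randomised comparison.
3. **Optional:** if a randomised comparison of facial weakness is wanted, compare its incidence between arms using the cranial nerve VII examination scheduled for all arms at weeks 12, 24 and 36. This requires the case report form to record the finding in the same way in TAU as in the injection arms. State two limits: assessment is open-label, and examinations 12 weeks apart may miss weakness that comes and goes between them.

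Items 1 and 2 cost only wording and should be settled before any comparative analysis. They lose no outcome listed in 3.3.2, since FaCE is not there. Item 3 may need a case report form change and is not required to resolve the contradiction.

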	To compare the proportion of participants achieving more than 30% and more than 50% reductions in pain intensity, as well as 30% and 50% improvements in quality of life, across treatment groups at 36 weeks	Disorder-specific quality of life measured by Oral Health Impact Profile-TMDs (OHIP-TMD) and Characteristic Pain Intensity (CPI) at baseline and 36 weeks.
	To examine responder rates and adherence over time in all interventions	Routinely collected descriptive data. Longitudinal sequential qualitative data collection from purposive subsample of participants.
	To evaluate whether any of the interventions affect jaw function	Jaw function limitation questionnaire short-form administered at screening, 12, 24 and 36 weeks.
	To evaluate whether any of the interventions affect psychosocial distress, sleep quality, or analgesia use	PHQ-4, psychosocial distress administered at screening, 12, 24 and 36 weeks. Brief Pittsburgh Sleep Quality Index administered at screening, 12, 24 and
		36 weeks. Over-the-counter (OTC) analgesia use. Data collected from patient at screening, 12, 24 and 36 weeks
	To compare the adverse effect profiles of the interventions including changes in the	Structural TMJ changes on MRI and apparent diffusion coefficient as a marker of bone density. Serum

IRAS ID: 1008152

	1	T	
	temporomandibular joint (TMJ) using MRI and biomarkers.	biomarkers of bone turnover (CTX and P1NP). Measured from screening visit (visit 1) up to 36 weeks.	
	To explore treatment experiences and acceptability of interventions	Longitudinal sequential qualitative data collection from participants	
		Global impression of change at 36 weeks.	
		Liverpool adverse effects profile. AE or SAE reporting from informed consent up to 36 weeks.	
Exploratory	Explore participants' reporting	Pain tolerance and threshold to a	
	accuracy of pain intensity in response to a controlled pressure	pressure stimulus and participant's reported pain intensity.	
	stimulus.	R ² values derived from regression of	
	Explore the influence of pain reporting accuracy on outcome in	applied stimulus and reported pain intensity.	
	the trial.		
Investigational Medicinal Product(s)	Oral gabapentin		
	Oral amitriptyline		
	As this is a pragmatic trial any brand of the oral medication can be used		
	Injectable therapy to bilateral masset	er and temporalis muscles:	
	- Intra-muscular lidocaine 2%,	2mls with or without preservative	

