8.6. Concomitant Medications

Simple analgesia (Ibuprofen, Aspirin, Paracetamol, co-codamol) are permitted and will be recorded via the database at screening (Visit 1) and throughout the trial. Use of prescribed opiates for a non TMD event should be reported in the database and a risk assessment considered if the participants are receiving Treatment As Usual, to determine if there are any risks associated with contraindicated medications. All repeat medications will also be recorded in the clinical notes and database.

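### Analgesia use is analysed as one any-time binary without screening use, which costs precision and lets markedly unequal attrition look like a treatment effect

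*Protocol*

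**What the plan says.** Protocol section 10.2.2 fixes the outcome and the type of model: "Analgesia use at any time during the trial will be analysed as a binary outcome using mixed effects logistic regression". Site enters as the random term; the only fixed terms are treatment arm and psychosocial stratum. There is no term for screening use and none for timepoint.

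The data would support more. The trial summary lists "Over-the-counter (OTC) analgesia use. Data collected from patient at screening, 12, 24 and 36 weeks". Section 7.4.2 records at the screening visit "analgesia use in the last month and reason". The schedule of events (7.4.10) repeats the analgesia enquiry at the medical review at weeks 12, 24 and 36. Section 8.6 confirms that "Simple analgesia (Ibuprofen, Aspirin, Paracetamol, co-codamol) are permitted" during the trial.

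The same paragraph of 10.2.2 treats its other outcomes differently. The patient-reported scales get a mixed model like that of the co-primary outcomes, "but with the baseline value of the corresponding outcome included as a fixed effect". The 30% and 50% responder outcomes "will be analysed separately at each timepoint using mixed effects logistic regression", with baseline score as a covariate.

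The intention-to-treat set (10.1) keeps anyone with at least one assessment after baseline, so participants enter with one, two or three follow-ups.

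**The concern.** Two features of the stated model matter.

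First, screening use is likely to predict later use well. It is collected and then left out. In a randomised comparison this does not bias the test, but it gives away precision at no saving.

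Second, whether a participant is ever recorded as a user depends on how often he or she is asked. An arm that loses more people has fewer occasions to record use and can look as if it uses less. The co-primary models use all timepoints to help with missing data (10.2.1). This model has no such device, and section 10.2.3 deals only with missing items within instruments.

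At stake is one secondary objective, whether the treatments affect analgesia use (3.2 e).

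**Working it through.** **The protocol's own figure.** Section 10.3 gives no calculation for analgesia use, only for OHIP-TMD. Difference 6.0, SD 20.7, two-sided 5%, 90% power: 2 × (1.960 + 1.282)² × 20.7² / 6.0² ≈ 250.1, so 251 per arm. Then 251 × (1 − 0.6²) = 160.6, so 161; 161 / 0.73 = 220.5, so 221; 3 × 221 = 663. This reproduces and is untouched by the present point.

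**Assumptions.** The protocol gives no use rates, no within-person correlation and no loss by arm. All are assumed here, using a random-intercept logistic model for use at each visit. Site and stratum effects are left out.

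**Dependence on visits observed.** With k visits, P(ever) = 1 − E[(1 − p)^k], where logit p = b + s·Z and Z is standard normal. At 50% use per visit and s = 2.5, P(ever) is 50.0%, 63.1% and 69.7% for k = 1, 2 and 3.

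**No true effect, missed visits counted as non-use.** Take loss of 15% v 39%, all after week 12:
- lower-loss arm: 0.15 × 0.500 + 0.85 × 0.697 = 66.7%
- higher-loss arm: 0.39 × 0.500 + 0.61 × 0.697 = 62.0%
- odds ratio (0.667/0.333) / (0.620/0.380) = 1.23

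Over per-visit use of 30-80% and s of 1.5-3.5, with 221 per arm:

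| Loss by arm | Spurious difference (points) | Odds ratio | Type I error |
|---|---|---|---|
| 27% v 27% | 0 | 1.00 | 5% |
| 20% v 34%, spread over visits | 0.9-2.5 | 1.06-1.24 | 6-9% |
| 15% v 39%, spread over visits | 1.6-4.4 | 1.10-1.47 | 8-19% |
| 15% v 39%, all after week 12 | 2.4-6.4 | 1.15-1.64 | 11-32% |

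Separate simulations (221 per arm, about 65% use at baseline) gave about 13-25% at 10% v 35% loss, against about 5% for a per-visit analysis with baseline use. At 20% v 30% they gave 6-7%, against 5-6%.

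**Does a scoring rule cure it?** In the 15% v 39% example, suppose incomplete follow-up with no reported use is set to missing and any reported use is kept:
- 0.667 / (1 − 0.15 × 0.5) = 72.1%
- 0.620 / (1 − 0.39 × 0.5) = 77.0%
- odds ratio 0.77

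The spurious effect changes direction and does not go away.

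**Power, adding screening use to the any-time model.** With 161 per arm, a constant 15-point fall in per-visit use and s of 1.5-3.5, power rises from 76-85% to 78-94%, a gain of 2 to 14 points. With 221 per arm, log odds ratio −0.8 and equal 27% loss, it rises from 68% to 75% at s = 2 and from 44% to 58% at s = 3.

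**Power, any-time use against per-visit analyses.** With 221 per arm, log odds ratio −0.8 constant over visits, equal 27% loss and s = 2:
- any-time use as planned: about 68-70%
- effect pooled over visits, with baseline use: about 95%
- week-36 contrast, with baseline use: 66-67%

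At s = 1.2, any-time use gives 86% and the week-36 contrast 82%. If the effect instead builds up (0, 50 and 100% of its size at weeks 12, 24 and 36; 161 per arm), unadjusted any-time use has 18-27% power, unadjusted week-36 use 76-79%, and adjusted week-36 use 78-93%.

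**The case against.** Any-time use is a legitimate and simple outcome, and moving to use per visit changes the question. The protocol states no differential loss. Its 27% is described as a worst case, and with equal loss there is no bias. Stopping treatment does not mean leaving follow-up: sections 7.5 and 7.6 keep such participants in assessment and seek week 36 as a minimum. Section 8.6 has analgesia recorded throughout the trial, so use around a missed interim visit may still be captured later. How missed visits are scored may be settled in the SAP, which is not at hand.

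Most of this stands, and it limits the size of the point. It does not answer the omission of screening use, which the protocol fixes itself. Nor does a scoring rule remove the dependence on visits observed, as the reversal from 1.23 to 0.77 shows.

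A reader might also infer that collapsing to any-time use always loses power, perhaps because nearly everyone in this population will have used an analgesic. The documents give no use rates to support near-saturation. Under a constant effect, any-time use does about as well as the week-36 contrast. The 95% belongs to an analysis pooled over visits.

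**Conclusion.** The point holds in a limited form. Omitting screening use is a needless loss of precision, about 2 to 14 power points under the assumed rates, and is out of line with the outcomes beside it. The any-time definition can turn attrition into an apparent effect, but only when loss differs between arms. The distortion is small at 20% v 30% (type I error 6-7%) and material at 10% v 35% (about 13-25%). To say that the planned analysis will produce a false effect would go beyond the documents, because no loss by arm is stated. A large power loss from the collapse itself arises against a visit-averaged effect, or if the effect builds up over the cycles, and the protocol assumes no particular pattern.

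All sizes rest on assumed use rates, within-person correlation and loss. The co-primary analyses and the sample size are unaffected.

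**What to change.** In section 10.2.2, replace the analgesia sentence with a repeated-measures logistic mixed model for use at weeks 12, 24 and 36. It would have random effects for site and participant, and fixed effects for treatment, timepoint, their interaction (needed for the week-36 contrast), screening analgesia use and psychosocial stratum. Report the treatment effect averaged over visits alongside the week-36 contrast, and keep any-time use as a descriptive table. If any-time use is to stay as the analysed outcome, at least add screening use as a fixed effect.

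The cost is about one sentence, and all the data are already collected. There are three downsides. The question changes from any use to use per visit. The week-36 contrast alone gains no power over any-time use if the effect is constant. The model also relies on data being missing at random, as the co-primary models do.
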